Clinical Study Protocol: NAV3-21

Study Title: An Evaluation of the Safety of Escalating Doses of Tc 99m Tilmanocept by Intravenous (IV) Injection and Skeletal Joint Imaging with SPECT in Subjects with Active Rheumatoid Arthritis (RA) and Healthy Controls

Study Number: NAV3-21

Study Phase: 1 and 2

Product Name: Technetium Tc 99m tilmanocept

IND Number: 132943

Investigator(s): Multicenter

Sponsor: Navidea Biopharmaceuticals, Inc
[name]

Sponsor Contact: [name]
Associate Clinical Research Project Manager
[contact]

Medical Monitor: [name]
Senior Medical Director
[contact]

Date

Original Protocol: 23 May 2016

Amendment 1: 12 September 2016

Amendment 2: 22 December 2016

Amendment 3: 09 February 2017

Amendment 4: 23 August 2017

Amendment 5: 18 April 2018

Amendment 6: 19 June 2018

Confidentiality Statement

This document and its contents are the property of and confidential to Navidea Biopharmaceuticals. Any unauthorized copying or use of this document is prohibited.

SYNOPSIS

Study title	An Evaluation of the Safety of Escalating Doses of Tc 99m Tilmanocept by Intravenous (IV) Injection and Skeletal Joint Imaging with SPECT in Subjects with Active Rheumatoid Arthritis (RA) and Healthy Controls
Study phase	Phase 1 and 2
Study objective(s)	
Primary
 
Determine the safety and tolerability of escalating doses of Tc 99m tilmanocept. 
Secondary
 
Determine the localization of Tc 99m tilmanocept by SPECT (single photon emission computed tomography) imaging in subjects with active RA and asymptomatic controls and concordance of localization with clinical symptomology.Comparison of localization intensity between Tc 99m tilmanocept dose groups for optimal dose selection and determination of optimal imaging time.To estimate the pharmacokinetics (PK) and dosimetry of Tc 99m tilmanocept in subjects with and without active RA.
Duration of treatment	Up to 53 days
Study drug	Technetium Tc 99m tilmanocept
Dose(s) and Route of administration	
Route of Administration: All administrations of Tc 99m tilmanocept will occur through an intravenous (IV) route of injection. For the 50 and 200 µg doses a single syringe will be used and injected as a slow push into the Y-port. For the 400 µg dose 2 syringes will be used and injected sequentially as a slow push into the Y-port. At the completion of the injection(s), a 10 cc sterile normal saline flush will be administered.
 
The preferred site of IV placement will be the left or right antecubital vein unless both elbows are primary sites for RA imaging, and then the site for IV placement will be between the elbow and the wrist.
 
Doses: Tc 99m tilmanocept will be received by subject through IV administration at one of 3 mass doses: 50 µg, 200 µg, or 400 µg. Within each mass dose group, subjects will receive Tc 99m tilmanocept labeled with one of 3 radiolabel doses: 1 mCi, 5 mCi, or 10 mCi.

	Tilmanocept Mass Dose			
	Specific Radioactivity	50 µg	200 µg	400 µg
	10 mCi	Group 1 n = 3 RA	Group 2 n = 3 RA	Group 3 n = 3 RA
	5 mCi	Group 4 n = 3 RA	Group 5 n = 3 RA	Group 6 n = 3 RA
	1 mCi	Group 7 n = 3 RA	Group 8 n = 3 RA	Group 9 n = 3 RA
	
* Group 10 will consist of 6 Healthy Controls (HC) (3 female subjects and 3 male subjects) and Group 11 will consist of 6 subjects with active RA (3 female subjects and 3 male subjects). Subjects in Groups 10 and 11 will be enrolled in parallel and will be dosed at the maximum tolerated dose (MTD) as determined from Groups 1-9.
			
Inclusion criteria	
ALL SUBJECTS:
 
 1. The subject has provided written informed consent with HIPAA (Health Information Portability and Accountability Act) authorization before the initiation of any study-related procedures. 2. Has a negative urine drug screening for illicit or unprescribed drugs suggestive of drug abuse as determined by the investigator. 3. All subjects shall be ≥18 years of age at the time of consent. 
CONTROL SUBJECTS:
 
 4. The subject is deemed to be clinically free of any inflammatory disease (s) and has not experienced joint pain for at least 4 weeks prior to the consent date. 
ACTIVE RHEUMATOID ARTHRITIS SUBJECTS:
 
 4. The subject has moderate to severe RA as determined by the 2010 ACR/EULAR (score of ≥ 6/10) that includes an affected hand and at least one large jointing (elbow, knee or shoulder). 5. The subject has a DAS28 of ≥ 3.2 (includes the Erythrocyte Sedimentation Rate [ESR] test and Visual Analog Scale [VAS]) . 			

	
 6. If the subject is receiving methotrexate, they have been at a stable dose for > 4 weeks prior to the Baseline Visit 2 (Day 1). 7. If the subject is receiving biologic therapy, they have been at a stable dose > 8 weeks prior to the Baseline Visit 2 (Day 1). 8. If the subject is receiving NSAIDS (nonsteroidal anti-inflammatory drug) or oral corticosteroids, the dose has been at a stable dose for > 4 weeks prior to the Baseline Visit 2 (Day 1). The corticosteroid dose should be ≤ 10mg/day of prednisone or an equivalent steroid dose.

Exclusion criteria
	
 1. The subject is pregnant or lactating. 2. The subject size or weight is not compatible with imaging per the investigator. 3. The subject has had or is currently receiving radiation therapy or chemotherapy for a condition other than rheumatoid arthritis. 4. The subject has renal insufficiency as demonstrated by serum creatinine clearance of < 60 mL/min. 5. The subject has hepatic insufficiency as demonstrated by ALT (alanine aminotransferase [SGPT]) or AST (aspartate aminotransferase [SGOT]) greater than two times the upper limit of normal. 6. The subject has a chronic or persistent infection or has any condition that would, in the opinion of the examining physician, preclude their participation. 7. The subject has a known allergy to or has had an adverse reaction to dextran exposure. 8. The subject has received an investigational product within 30 days prior to the Tc 99m tilmanocept administration. 9. The subject has received any radiopharmaceutical within 7 days prior to the administration of Tc 99m tilmanocept.

Study design
	
Prospective, open-label, multicenter, dose escalation, and safety with PK and dosimetry study of injected Tc 99m tilmanocept in the detection of and assessment of localization to skeletal joints in subjects with and without active RA by SPECT imaging. All subjects will receive IV administration at one of 3 mass doses: 50 µg, 200 µg, or 400 µg. Within each mass dose group, subjects will receive Tc 99m tilmanocept labeled with one of 3 radiolabel doses: 1 mCi, 5 mCi, or 10 mCi.
 
All subjects will have a whole body planar SPECT scan. Subjects enrolled in Groups 1-9 will receive a whole body

	
planar SPECT scan followed by a 3D SPECT or SPECT/CT scan on areas of interest at two specified time points post injection: 60 minutes \pm 15 minutes and 180 minutes \pm 15 minutes. Subjects enrolled in Groups 10-11 will receive a whole body planar SPECT scan performed at 4 specified time points post injection: 15 \pm 5 minutes, 60 \pm 15 minutes, 180 \pm 15 minutes and 18-20 hours. Subjects enrolled in Groups 10-11 will also receive a planar SPECT hands scan at 60 \pm 15 minutes and 180 \pm 15 minutes post-injection. PK blood sampling will be performed before injection (within 15 minutes), immediately following injection (within 5 minutes), and at each scanning timepoint. Dosimetry tests will be performed at each scanning timepoint. PK of urine will be assessed through counts of the bladder wall obtained from cumulative quantitative planar imaging from radiation dosimetry.

Methodology	
The study includes: screening, enrollment, pre- and post-injection assessments, injection, imaging and follow-up.
 
All Subjects:
 
Visit 1, Screening (Day -44 to Day 0): The screening visit will include informed consent, preliminary review of study eligibility, collection of medical history including medications, urine drug screen, vital signs, ECG (electrocardiogram), physical exam including height and weight, clinical labs, RA specific labs, urinalysis, urine pregnancy test for subject of childbearing potential, 2010 ACR/EULAR score, DAS28 evaluation.
 
Groups 1-9:
 
Visit 2, Baseline (Day 1): Pre-Tc 99m Tilmanocept Injection:
 
• Before injection (Day 1)
○ Urine pregnancy test will be performed for subjects of childbearing potential○ Concomitant medication review○ ECG - within 15 minutes prior to injection○ Vital Signs - within 15 minutes prior to injection

	
Tc 99m Tilmanocept Injection : Subjects will receive their open label serial dose assignment in accordance with Table 1. Adverse event monitoring will continue through completion of the trial.
 
Post-Tc 99m Tilmanocept Injection:
 
• 0 - 15 Minutes Post Injection:
○ Assessment of adverse events○ ECG (completed before vital signs)○ Vital Signs• 60 ± 15 Minutes Post Injection:
○ Assessment of adverse events○ Whole body planar imaging○ Planar image with both hands in the field of view (FOV)
▪ Additional 3D SPECT or SPECT/CT will be obtained on identified joints of interest.• 180 ± 15 Minutes Post Injection
○ Assessment of adverse events○ Whole body planar imaging○ Planar image with both hands in the FOV
▪ Additional 3D SPECT or SPECT/CT will be obtained on identified joints of interest. 
5± 2 Days Post-injection Follow-Up Visit (Visit 3):
 
• Vital Signs• ECG• Physical Exam, including body weight• Clinical labs and urinalysis• Concomitant medication review• Assessment of adverse event
--	---

Groups 10-11:

Visit 2, Baseline (Day 1):

Pre-Tc 99m Tilmanocept Injection:

- Before injection (Day 1)
 - Urine pregnancy test will be performed for subjects of childbearing potential
 - Concomitant medication review
 - ECG - within 15 minutes prior to injection
 - Vital Signs - within 15 minutes prior to injection
 - PK blood sample – within 15 minutes prior to injection

Tc 99m Tilmanocept Injection: Subjects will receive the maximum tolerated dose, as determined from [Table 1](#). Immediately following Tc 99m tilmanocept administration, a PK blood sample will be drawn. Adverse event monitoring will continue through completion of the trial.

Post-Tc 99m Tilmanocept Injection Procedures:

- 0 - 15 Minutes Post Injection:
 - Assessment of adverse events
 - ECG (completed before vital signs)
 - Vital Signs
- 15 ± 5 Minutes Post Injection:
 - Whole body planar imaging
 - PK blood sampling
 - Assessment of adverse events
- 60 ± 15 Minutes Post Injection:
 - Whole body planar imaging
 - Planar image with both hands in the FOV
 - PK blood sampling
 - Assessment of adverse events
- 180 ± 15 Minutes Post Injection:
 - Whole body planar imaging
 - Planar image with both hands in the FOV
 - PK blood sampling
 - Assessment of adverse events

	
Post-Tc 99m Tilmanocept Injection Procedures and Follow-Up Visit (Visit 3):
 
 • 18-20 Hours Post Injection: 
 ○ Whole body planar imaging ○ PK blood sampling ○ Vital Signs ○ ECG ○ Physical Exam, including body weight ○ Clinical labs and urinalysis ○ Concomitant medication review ○ Assessment of Adverse Events 	

Planned study dates
	
Start of study recruitment / August 2016
	
End of Recruitment/July 2018 End of Study/September 2018

Planned number of study centers
	
Approximately 1-3 centers in the United States
	

Number of subjects
	
Up to 48 evaluable subjects may be enrolled. The dose escalation portion of this study is a modified 3+3 design with no dose de-escalation. The sequential cohort enrollment characteristics of this design do not allow a fixed computation of sample size. The parameters of the design that can be calculated are shown in Table 4. Based on an assumed vector of probabilities of no subjects experiencing pharmacologic activity or an Adverse Drug Reaction (ADR) in each dose group, the average sample size of the dose escalation phase of the study is n=26.3 patients and the probability that dose group 7 will be selected as the MTD (maximum tolerated dose) is 0.152.
	

Primary endpoint
	
Proportion of subjects not experiencing pharmacologic activity or ADR in each dose group.
	

Secondary endpoints
	
The secondary endpoints for this study are:
 
 • Per subject localization rate of Tc 99m tilmanocept by SPECT imaging • Per joint location clinically RA-identified joint localization rate of Tc 99m tilmanocept by SPECT imaging • Concordance of Tc 99m localization with anatomical areas of active RA defined by clinical symptomology. • Localization intensity for each clinically RA-defined joint (as determined by quantitative SPECT gamma counts) 	

	
 • Per subject localization rate of Tc 99m tilmanocept in areas other than RA-positive joints by SPECT imaging • The following PK parameters will be calculated, whenever possible, using Tc 99m tilmanocept total radioactivity in whole blood and urine: maximum observed concentration (C_{max}), time to C_{max} (t_{max}), area under the concentration-time curve (AUC) from Hour 0 to the last measureable concentration (AUC_{0-t}), AUC extrapolated to infinity ($AUC_{0-\infty}$), apparent terminal elimination rate constant (λ_z), and apparent terminal elimination half-life ($t_{1/2}$). • Radiation dosimetry of Tc 99m tilmanocept will include radiation doses per organ ($\mu Gy/MBq$), organs receiving the highest organ dose (HT), effective doses per organ ($\mu Sv/MBq$), mean effective dose ($\mu Sv/MBq$), effective dose resulting from a diagnostic dose $\pm 20\%$. Dosimetry will be based on target organ image counts and modeling per OLINDA/EXM® 2.0 (Organ Level INTERNAL Dose Assessment/EXponential Modeling) software.

Data Analyses
	
The following analysis population will be defined for the study:
 
 • Intent-to-Diagnose (ITD) Population - Subjects who are enrolled in the study in Groups 1-9, injected with Tc 99m tilmanocept, and received whole body planar imaging will be included in the ITD analysis population. • Radiopharmacokinetic (RPK) Population – Subjects that have been enrolled in the study in Groups 10-11, injected with Tc 99m tilmanocept, and received whole body planar imaging will be included in the RPK analysis population. • Safety Population – All patients who are enrolled and injected with Tc 99m tilmanocept in the study will be included in the safety population. • Per Protocol (PP) Population – The PP population will include all safety subjects without major protocol violations. 
All safety data analyses will be conducted on the safety population. All efficacy data analyses will be conducted on the ITD and PP population with the ITD population being the primary analysis set. All analyses of RPK data will be carried out on the RPK population.

	
The number and percentage of subjects experiencing pharmacologic activity or ADRs will be tabulated by dose group and overall.
 
Per subject localization rates and percentage will be calculated by time point by dose group and overall.
 
Per joint location localization rates and percentages will be calculated by time point by dose group and overall.
 
Per location concordance of clinical diagnosis to nuclear medicine specialist illumination indication will be computed across all RA positive sites of all subjects at all time points.
 
Localization intensities will be summarized by descriptive statistics (mean, median, standard deviation, minimum, maximum and range) by joint location at each time point.
 
Radiopharmacokinetic (RPK) parameters will be estimated for each subject using noncompartmental models. Summary statistics (n, mean, std, CV, geometric mean) will be computed for each RPK parameter across all subjects by Group (10, 11).
 
For dosimetry data, for each dosimetry parameter, summary statistics (n, mean, std, and a one standard deviation width confidence interval) will be computed by organ type and across all subjects by Group (10,11).

--	--

TABLE OF CONTENTS

SYNOPSIS.....	2
LIST OF IN-TEXT TABLES	13
LIST OF APPENDICES.....	14
LIST OF ABBREVIATIONS AND DEFINITIONS OF TERMS.....	15
STUDY ADMINISTRATIVE STRUCTURE.....	19
1 INTRODUCTION	20
1.1 Background.....	20
1.2 Preliminary Data	23
1.3 Previous Nonclinical Research and Clinical Trial Experience Tilmanocept and Lymphoseek.....	25
1.3.1 Nonclinical Evaluations – Injection Site Subcutaneous	25
1.3.2 Nonclinical Evaluations – IV AND IP Administration	26
1.3.3 Clinical Pharmacokinetics and Pharmacodynamics	29
1.3.4 Clinical Efficacy	29
1.3.5 Clinical Safety.....	30
2 STUDY OBJECTIVES.....	31
2.1 Primary Objective(s).....	31
2.2 Secondary Objective(s).....	31
3 OVERVIEW OF METHODOLOGY AND DESIGN.....	32
3.1 Overall Study Design.....	32
3.2 Justification for Study Design and Population.....	32
3.3 Protocol Adherence.....	33
3.4 Study Duration	33
4 STUDY POPULATION	34
4.1 Eligibility	34
4.1.1 Inclusion Criteria	34
4.1.2 Exclusion Criteria	35
4.2 Recruitment.....	35
4.3 Withdrawal.....	35
4.4 Replacement.....	36
4.5 Subject Identification	36
5 INVESTIGATIONAL PRODUCT.....	37
5.1 Identification of Investigational Product	37
5.2 Investigational Product Dosage and Administration	37
5.3 Treatment Assignment.....	38
5.4 Packaging and Labeling.....	38

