5.3 Treatment Assignment

In this open-label, non-randomized, multicenter, dose-escalation safety study all subjects will receive IV administration at one of 3 tilmanocept mass doses: 50 µg, 200 µg, or 400 µg. Within each mass dose group, subjects will receive tilmanocept labeled to one of 3 radiolabel Tc 99m doses: 1 mCi, 5 mCi, or 10 mCi.

Group 1 will be the starting dose group. Three subjects will be enrolled into Group 1. If none of the 3 subjects experiences pharmacologic activity or an ADR, 3 subjects will be enrolled in Group 2. However, if one of the first three subjects experiences a pharmacologic activity or an ADR, three more subjects will be treated at the same dose level. If 2 out of 3 or 3 out of 6 subjects experiences a pharmacologic activity or an ADR in Group 1 the MTD cannot be determined. If no additional pharmacologic activity or ADRs are observed in the expanded group, the dose escalation will continue. If one additional pharmacologic activity or ADR is observed, the current dose will be deemed the maximum tolerated dose (MTD). If more than one additional pharmacologic activity or ADR is observed in the expanded group, the previous dose will be deemed the MTD. Dose escalation will continue until the MTD is found or until Group 9 is reached with only one ADR or without any ADRs. If no ADRs are experienced from Groups 1-9, then the MTD will be highest tilmanocept mass dose radiolabeled at the highest level (400 µg/10 mCi).

Group 10 will consist of 6 HC subjects and Group 11 will consist of 6 subjects with active RA. Subjects enrolled in Groups 10 and 11 will be dosed at the dose level that is established as the MTD from Groups 1 through 9. The maximum tolerated dose is defined as the dose below where >33% of subjects experienced an ADR.

NOTE: Adverse Drug Reaction

An Adverse drug reaction (ADR) includes all noxious and unintended responses to a medicinal product related to any dose or dose regimen. The phrase “responses to a medicinal product” means that a casual relationship between a medicinal product and an adverse event is at least a reasonable possibility, i.e. the relationship cannot be ruled out.

In this multi-center trial, doses will be serially assigned in an open label fashion in accordance with [Table 1](#). Investigators who have identified a subject for participation will receive the dose assignment from the sponsor and request that dose from the supporting Cardinal Health pharmacy.

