8 PROCEDURES AND VARIABLES

8.1 Population Characteristics

8.1.1 Demographic and Other Baseline Characteristics

Up to 48 evaluable subjects may be enrolled. Up to thirty-six (36) female or male subjects ≥ 18 years of age with evidence of active RA will be enrolled in Groups 1-9. Three (3) female and three (3) male subjects aged ≥ 18 without evidence of active RA (HC) will be enrolled in Group 10. Three (3) female and three (3) male subjects aged ≥ 18 with evidence of active RA will be enrolled in Group 11.

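### The stated ceiling of 36 subjects in Groups 1-9 (48 in total) is not reconciled with the Section 5.3 expansion rule, which allows up to 54 (66); the chance that it matters is about 3%

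*Combined protocol and SAP*

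**What the plan says.** **Stated size.** The Synopsis (Number of subjects) and Section 8.1.1 both state: "Up to 48 evaluable subjects may be enrolled". Section 8.1.1 divides the total: "Up to thirty-six (36) female or male subjects" with active RA in Groups 1-9, then six in Group 10 and six in Group 11.

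**Escalation rule, Section 5.3.** Each group opens with three subjects. If one of the three has an event (pharmacologic activity or an ADR), "three more subjects will be treated at the same dose level". After that, "If no additional pharmacologic activity or ADRs are observed in the expanded group, the dose escalation will continue". One further event makes the current dose the MTD; more than one makes the previous dose the MTD. The end condition is: "Dose escalation will continue until the MTD is found or until Group 9 is reached with only one ADR or without any ADRs".

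**Operating characteristics, Section 9.4.** Table 4 gives an assumed event probability for each group, the probability that each dose is the MTD, and an average escalation-phase size of 26.3. The text says the sequential design permits no fixed sample-size computation. It does not derive 36 or mention a cap.

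**The concern.** Two parts of the protocol bound the size of Groups 1-9, and the bounds differ. The figure 36 equals 27 + 3 × 3, that is, nine groups of three plus three expansions. Section 5.3 does not limit expansions to three. It ends escalation on finding the MTD or on reaching Group 9, not on an enrolment count.

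If the count reaches 36 with the rule still running, the text gives two incompatible instructions: stay within the stated size, or continue. The MTD is the statistical objective named in Section 9, and it is the dose given to Groups 10 and 11. A halt at the ceiling would therefore leave that dose undefined by the protocol's rule.

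**Working it through.** **Inputs.** Nine groups, cohorts of three, and the expansion and MTD rules (Section 5.3). Event probabilities .01, .02, .05, .08, .10, .13, .16, .19, .22 (Table 4). Groups 10 and 11: 6 + 6 = 12 (Section 5.3).

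**Step 1: reproduce Table 4.** For a group with event probability p, the first three subjects give

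- no event: a0 = (1 − p)³
- one event (expand): a1 = 3p(1 − p)²
- two or more: a2 = 1 − a0 − a1

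The probability of escalating is a0 + a1·a0. The current dose is the MTD with probability a1·a1. The previous dose is taken with probability a2 + a1·a2. (Section 5.3 spells out two events in the first three only for Group 1. In later groups I take it to select the previous dose, and the match below supports this.) With R the probability of reaching a group, its average size is R(3 + 3·a1). No cap is applied.

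| Group | 1 | 2 | 3 | 4 | 5 | 6 | 7 | 8 | 9 |
|---|---|---|---|---|---|---|---|---|---|
| P(MTD), stated | .002 | .012 | .039 | .071 | .103 | .136 | .152 | .148 | .065 |
| P(MTD), computed | .002 | .012 | .039 | .071 | .103 | .136 | .153 | .148 | .065 |
| Average n, stated | 3.1 | 3.2 | 3.4 | 3.5 | 3.3 | 3.2 | 2.8 | 2.2 | 1.6 |
| Average n, computed | 3.09 | 3.17 | 3.39 | 3.49 | 3.38 | 3.19 | 2.81 | 2.29 | 1.71 |

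The MTD probabilities agree to within .001. The average total is 26.5 against the stated 26.3. A cap at 36 does not explain that gap: Group 5 already differs, and at most 5 × 6 = 30 subjects can be enrolled by then.

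**Step 2: can Group 9 expand?** The end condition could be read as stopping on arrival at Group 9, which would give maxima of 8 × 6 + 3 = 51 and 51 + 12 = 63. Table 4 does not fit that reading. With R = .406 and a1 = 3 × .22 × .78² = .4015, P(MTD = Group 9) = .406 × .4015² = .065, as stated, and it arises only through expansion. Without expansion the average in Group 9 would be 3 × .406 = 1.2, against the stated 1.6.

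**Step 3: the maximum.** One event in three and then none in three, in each of Groups 1-8, followed by an expanded Group 9, gives 9 × 6 = 54. Adding 12 gives 66, before any replacements under Section 4.4.

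**Step 4: when 36 is exceeded.** If g groups open and k of them expand, N = 3g + 3k, so N > 36 requires g + k > 12:

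- Group 9 opened: four or more expansions, counting Group 9's own
- escalation ending in Group 8: five or more
- escalation ending in Group 7: six or more
- ending earlier: impossible

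**Step 5: how likely.** Exact distribution under Table 4's probabilities:

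| N in Groups 1-9 | Probability |
|---|---|
| 36 | .0743 |
| 39 | .0227 |
| 42 | .0044 |
| 45 | .0005 |
| 48 or more | below .0001 |

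P(N > 36) = .0276 and P(N ≥ 36) = .102. A single cohort beyond 36 accounts for .0227/.0276 = 82% of the excess. P(N = 54) = 1.6 × 10⁻⁸.

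Flat event rates are my assumption, used to show sensitivity:

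| Flat rate | 2% | 5% | 10% | 12% | 15% | 20% |
|---|---|---|---|---|---|---|
| P(N > 36) | .001 | .013 | .040 | .042 | .036 | .018 |

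**The case against.** The strongest reply is that 36 and 48 are administrative ceilings, not derived maxima. The sum 36 + 6 + 6 = 48 is correct, the wording is permissive, and the protocol says that no fixed size can be computed. The sponsor issues every dose assignment (Section 5.3) and so would see the count coming, and Section 3.3 provides for a formal amendment. The ceiling also covers about 97% of paths under Table 4.

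Most of this stands, and it limits the weight of the point. It does not remove the inconsistency. A ceiling still has to fit the stopping rule, and Section 5.3 has no stop for reaching one. A maximum can be computed even when the final size is random. An amendment would settle the matter only after the conflict had arisen.

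A reader might infer more, and the documents do not support it:

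- **That a fourth expansion before the last group forces a breach.** Four expansions by Group 8 give 24 + 12 = 36, which is within the ceiling. Under Table 4 a fourth expansion in Groups 1-8 has probability .0213, and 47% of those paths end at 36 or fewer. Conversely, .0164 of the .0276 (59%) comes from a fourth expansion in Group 9 itself.
- **That three expansions exhaust the ceiling.** They do so only if all nine groups open, and the count is then exactly 36, not above it.
- **That the trial is undersized by 18.** The difference 54 − 36 = 18 belongs to a path with probability 1.6 × 10⁻⁸.

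**Conclusion.** The stated size is wrong as written as a matter of internal consistency, and the severity is minor. The ceiling of 36 (48 in total) does not follow from the Section 5.3 rule, whose maximum is 54 (66 in total), and the protocol does not say how the two interact.

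The chance that this matters is about 2.8% under Table 4's assumed probabilities and 0.1-4.2% for flat rates of 2-20%. These figures assume independent subjects, a common event probability within each group, expansion allowed in every group, and no cap.

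It is not a failure of the sample size or of the design. Table 4's operating characteristics stand, and no endpoint or analysis changes.

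**What to change.** Reconcile the Synopsis and Section 8.1.1 with Section 5.3, in one of two ways:

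1. State 54 (Groups 1-9) and 66 (total) as the design maximum, and describe 36 and 48 as the expected upper range. Give the roughly 3% chance of exceeding that range beside the average in Section 9.4.
2. If 48 is a hard cap, reconcile it with the Section 5.3 rule, so that the protocol says how escalation and MTD selection work when the cap is reached. State in Section 9.4 that Table 4 assumes no cap.

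The documents do not settle which is intended, so the choice is the sponsor's. The first option restates a figure and, under Table 4, needs no subjects beyond 36 in Groups 1-9 on about 97% of paths. The second adds a few sentences, and possibly a rerun of Table 4 with the cap in place.
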